3.13.1.3. Methods for Missing Data Imputation

The missing measurement for KCCQ-CSS at 52 weeks for the primary estimand will be imputed through multiple imputation based on the reason for missingness.

- For missing measurements due to death, multiple imputation will be performed using the worst 15% observed data at 52 weeks from the same treatment group.
- For missing data due to all other ICEs or without ICE, retrieved dropout imputation will be applied, which will utilize observed data from participants in the same treatment group

who had outcome measures at Week 52 after early discontinuation of study drug to impute the missing value. In case there are not enough retrieved dropouts to provide a reliable imputation model, reference to the placebo imputation will be used.

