3.13.1.1.1. Estimand for the Endpoint

The estimand for the primary endpoint is described by the following attributes:

- Endpoint: change from baseline to Week 52 in KCCQ-CSS.
- Treatment condition of interest: tirzepatide MTD versus placebo.
- Handling of ICEs: using the treatment policy strategy to handle all ICEs.
- Population: all randomized participants.
- Population-level summary: the median difference between treatment arms.

The KCCQ is a 23-item, participant self-administered questionnaire that assesses impacts of HF "over the past 2 weeks" on 7 domains (Green et al. 2000; Joseph et al. 2013). Each of the 23 individual items are answered on Likert scales of varying length (5-point, 6-point, or 7-point scales). Domain scores are obtained by averaging the associated individual items and transforming the score to a 0 to 100 range. Higher scores indicate better health status. KCCQ-CSS is a summary score that is derived by taking the mean of the Physical Limitation and Total Symptom scores. Detailed scoring instructions are provided in Appendix 1, Section 5.1.

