3.13.1.4. Sensitivity Analyses for Kansas City Cardiomyopathy Questionnaire-Clinical Summary Score

For the primary endpoint of change from baseline in KCCQ-CSS, a mixed-effects model repeated measures (MMRM) analysis will be conducted to analyze the change from baseline in the KCCQ-CSS. The analysis will be guided by the treatment policy strategy. All values of the collected KCCQ-CSS data at baseline, 24 weeks, and 52 weeks will be used in the MMRM analysis. The primary endpoint assessment will be the contrast between tirzepatide and placebo at Week 52. The MMRM analysis will be repeated using data during the on-treatment period, which is considered as up to the last dose date plus 7 days.

The MMRM model will include treatment, time (Weeks 24 and 52), treatment-by-time interaction, stratification factors as fixed effects, and baseline value of the KCCQ-CSS as a covariate. Restricted maximum likelihood (REML) will be used to obtain model parameter estimates and the Kenward-Roger option will be used to estimate the denominator degrees of freedom. An unstructured covariance structure will be used to model the within-patient errors. If the analysis fails to converge, the following variance-covariance matrices will be used until convergence is achieved:

- heterogeneous Toeplitz
- heterogeneous first order autoregressive
- heterogeneous compound symmetry
- Toeplitz
- first order autoregressive, and
- compound symmetry.

In the MMRM analysis, the probability of missingness for any postbaseline KCCQ-CSS data that are not collected is assumed only to depend on the observed KCCQ-CSS values.

Change from baseline in the KCCQ-CSS will also be analyzed using an ANCOVA model. The ANCOVA model will include the categorical effect of treatment, stratification factors, and the continuous covariate of baseline KCCQ-CSS value. Missing KCCQ-CSS measurements at Week 52 will be imputed through multiple imputations as specified in Section 3.13.1.3.

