3.13.2.1.2. Main Analytical Approach

For the key secondary efficacy endpoints of change from baseline in 6MWD at Week 52, the same nonparametric approach as described in Section 3.13.1.1.2, and the same missing data imputation as described in Section 3.13.1.3, will be utilized.

3.13.2.2. Percent Change from Baseline in Body Weight Loss at Week 52

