3.13.2.2.2. Main Analytical Approach

The percent change from baseline in body weight will be analyzed using an analysis of covariance (ANCOVA) analysis. The ANCOVA model will include the categorical effect of treatment, stratification factors excluding baseline BMI group (<35, ≥35 kg/m²), and the continuous covariate of baseline body weight value.

Missing body weight data at the scheduled postbaseline visits will be imputed using the retrieved dropout approach (as described in Section 3.13.1.3) through multiple imputation. The final statistical inference over multiple imputations will be obtained using the method proposed by Rubin (1987).

3.13.2.3. Change from Baseline in High-sensitivity C-reactive Protein at Week 52

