3.13.2.3.2. Main Analytical Approach

Change from baseline in hsCRP will be analyzed using an ANCOVA model. The ANCOVA model will include the categorical effect of treatment, stratification factors, and the continuous covariate of baseline hsCRP value. The ANCOVA model will be based on the log-transformed values of hsCRP.

Missing hsCRP at the scheduled postbaseline visits will be imputed using the retrieved dropout approach (as described in Section 3.13.1.3) through multiple imputation. The final statistical inference over multiple imputations will be obtained using the method proposed by Rubin (1987).

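### SAP 3.13.1.3 imputes missing Week 52 values of participants known to be on study drug from participants who stopped it; a small donor mismatch that is cheap to remove

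*SAP*

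**What the plan says.** SAP 3.13.1.3 imputes missing Week 52 KCCQ-CSS in two branches. Deaths draw on the worst 15% of observed values in the same arm. The other branch takes everything else: "For missing data due to all other ICEs or without ICE, retrieved dropout imputation will be applied". Its donors are same-arm participants "who had outcome measures at Week 52 after early discontinuation of study drug to impute the missing value". If there are too few of them, "reference to the placebo imputation will be used".

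The KCCQ-CSS estimand in SAP 3.13.1.1.1 is defined by "using the treatment policy strategy to handle all ICEs", in all randomized participants. SAP 3.13 explains this as using observed values whether or not an intercurrent event has occurred.

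The rule carries to the key secondary endpoints:
- 6MWD (SAP 3.13.2.1.2): "the same missing data imputation as described in Section 3.13.1.3, will be utilized".
- Body weight (SAP 3.13.2.2.2): "Missing body weight data at the scheduled postbaseline visits will be imputed using the retrieved dropout approach".
- hsCRP (SAP 3.13.2.3.2): "Missing hsCRP at the scheduled postbaseline visits will be imputed using the retrieved dropout approach".

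**The concern.** Consider a participant who is still injecting at Week 52 and simply has no Week 52 questionnaire. Under treatment policy, the outcome this person would have contributed is an on-drug outcome. The rule supplies one from people who stopped, or from placebo. SAP 3.13.1.3 sets out to impute according to why the value is missing, yet it puts this reason together with drug discontinuation.

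Two effects could follow:

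1. **Shift in the estimate.** If benefit fades after stopping, imputed tirzepatide values are too low on average and the difference moves toward zero.
2. **Imputation variance.** Even without fading, a small group of retrieved dropouts has to supply values for more people, so the imputations vary more from one another.

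KCCQ-CSS starts at a two-sided 0.01 with roughly 80% power, and Protocol 9.2 states no allowance for missing data. What is at stake is some power and a slightly diluted estimate.

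**Working it through.** **Inputs from the documents** (Protocol 9.2): 350 per arm, mean change 5 versus 10, SD 19, two-sided alpha 0.01, Wilcoxon rank sum test, roughly 80% power.

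**The plan's own figure.** The standard error of the difference is 19 × √(2/350) = 1.436, so 5/1.436 = 3.481. With the Wilcoxon efficiency factor 3/π, 3.481 × √0.955 = 3.402. Subtracting 2.576 leaves 0.826, which is power of 79.6%. The stated power reproduces.

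**Assumptions, because the documents give no rates.** 12% of each arm is off drug by Week 52, and 60% of those are measured: 350 × 0.12 × 0.60 ≈ 25 donors per arm. Of the 308 on drug per arm, 1%, 2% or 5% lack the Week 52 value (about 3, 6 or 15 people). The overall difference is held at 5. The off-drug difference is 5 (no fade), 2.5 (half) or 0 (full). The on-drug difference is (5 − 0.12 × off-drug difference)/0.88, which is 5.68 under full fade.

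**Shift in the estimate.** Shift = 0.88 × rate × [(tirzepatide off − on) − (placebo off − on)].
- Full fade, no gap in placebo: 0.88 × 0.01 × 5.68 = 0.05 points at 1%, and 0.10 at 2%, out of 5. No fade: 0.
- Equal gaps in both arms: the bracket is zero and the shift cancels.
- Gaps that differ by 5 points between arms: 0.04 at 1% and 0.09 at 2%, in either direction.
- Body weight, with an on-drug difference of 15.5 points (inside the 15% to 16% in Protocol 2.2): 0.88 × rate × 15.5 × share of effect lost. Half to full fade gives 0.07 to 0.14 percentage points at 1% and 0.14 to 0.27 at 2%. This is no realistic power risk.

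**Power for KCCQ-CSS at 0.01.** Simulation used 8,000 trials per cell, eight equal strata, the van Elteren z pooled by Rubin's rules over 20 imputations (assumed), normal imputation without covariates, and no deaths. Gains over the SAP rule are in percentage points, for no / half / full fade:

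| On-drug participants missing | Half confirmed on drug (assumed) | All given on-drug donors (upper bound) |
|---|---|---|
| 1% | 0.3 / 0.8 / 0.9 | 0.5 / 1.4 / 1.7 |
| 2% | 0.8 / 1.4 / 2.1 | 1.2 / 2.8 / 4.1 |
| 5% (illustrative only) | 2.4 / 4.3 / 5.0 | 4.3 / 7.0 / 9.2 |

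The paired Monte Carlo error is 0.1 to 0.3 points. The no-fade entries are the donor-pool variance effect alone.

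- If all 0.05 were recycled to KCCQ-CSS (a favourable bound under SAP 3.13.3), the half-confirmed gain is 0.2 to 0.4 points at 1% and 0.3 to 0.9 at 2%.
- If the placebo fallback applies, the half-confirmed gain at 0.01 is 0.4 to 0.5 points at 1% and 0.8 to 0.9 at 2%.
- With no effect on or off drug, rejection at 0.01 is 0.9% to 1.2% under both the SAP rule and the split rule, and 0.5% to 0.8% under the fallback.

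**The case against.** **Treatment policy concerns observed values.** SAP 3.13 and 3.13.1.1.1 say what to do with data that exist; they do not dictate values for data never collected. A reader might infer that the SAP contradicts its own estimand. The documents do not support that. What does not fit is the estimator's missing-data assumption, and only for people known to be on drug.

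**The group is probably very small.** This stands. Participants who stop drug stay in the study and keep attending (Protocol 7.1.1). Leaving the study ends study drug (Protocol 7.2), so withdrawals belong under the current rule. A missed Visit 12 KCCQ or 6MWT is requested within 30 days (Protocol 8.1.1.1 and 8.1.2.1). No such request is stated for weight or hsCRP, although Protocol 8 allows repeat samples for technical issues.

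**On-drug participants who miss Week 52 may be doing worse than those who attend.** The rule names the no-event case explicitly, so it may be a deliberate and generally conservative choice. Preferring missing at random here is a judgement, and the documents cannot settle it.

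**The simulation is simplified.** It uses no covariates, and the SAP does not say that its imputation model has none. The variance effect is therefore a possibility whose size depends on that model.

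**A check already exists.** For KCCQ-CSS this is right: the all-data MMRM in SAP 3.13.1.4 follows treatment policy, uses Week 24 and avoids these donors. The ANCOVA there reuses them. For the key secondary endpoints, SAP 3.13.2.4 offers only on-treatment MMRMs, which target a different estimand, and a 6MWD ANCOVA with the same imputation. So 6MWD, body weight and hsCRP have no treatment-policy analysis free of these donors.

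**Conclusion.** The point holds as a cheap, low-priority improvement. A stated rule gives off-drug or placebo-type outcomes to participants who may be known to be on drug, and nothing requires it to.

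At 1% to 2% of on-drug participants missing, with half confirmed, the gain is about 0.3 to 2 power points for KCCQ-CSS at 0.01, and less if alpha is recycled. The estimate is diluted by at most about 0.10 of 5 points if placebo has no on-drug to off-drug gap. The off-drug share, retrieval rate, missing rate, confirmed share and degree of fade are all assumed.

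Two stronger readings are tempting and fail. One is that the rule materially underpowers the trial. Simulated power under the SAP rule at 1% missing is 71.8% to 72.5%, against 77.6% to 78.9% with complete data, but even the full split adds only 0.5 to 1.7 points. Most of the shortfall comes from missing off-drug values, which this change does not touch, and nothing in the documents supports the 5% row. The other is that the rule favours tirzepatide or raises false positives. Type I error is not inflated with no effect on or off drug. The expected shift under fading is toward no difference, though it can cancel or reverse.

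**What to change.** Split the second bullet of SAP 3.13.1.3.

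- **(a)** Participants who discontinued study drug, were interrupted at Week 52, or whose status cannot be confirmed: retrieved-dropout imputation as now, with the placebo fallback limited to this group.
- **(b)** Participants confirmed on drug: impute under missing at random from same-arm participants on drug at Week 52, using baseline, Week 24 where collected, and the stratification factors used for that endpoint.

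Confirmed should mean that the participant had not permanently discontinued and that the most recent recorded dose on or before the Week 52 target date lies within 7 days of that date. The on-treatment definition in SAP 3.13.1.4, "which is considered as up to the last dose date plus 7 days", should not be reused with the final dose date of the whole study. Drug can be interrupted and restarted (Protocol 6.6.1 and 6.6.2) and dosing continues after Visit 12 (Protocol 4.1), so someone off drug across Week 52 who later restarted would be classed as on drug.

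Apply the split to 6MWD, body weight and hsCRP, report the numbers imputed under (a) and (b) by arm, and keep the current rule as a sensitivity analysis.

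The cost is SAP wording and programming before unblinding, with no new data: dose dates are in the diary (Protocol 6.1). Participants due a combined Visit 12 and final visit may have no later visit to confirm status and would often stay in (a). So would silent dropouts, classed as lost to follow-up only at study end (Protocol 7.3). The analysis becomes slightly less conservative and assumes that confirmed on-drug participants with a missed value resemble their on-drug peers.

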3.13.1.4. Sensitivity Analyses for Kansas City Cardiomyopathy Questionnaire-Clinical Summary Score

For the primary endpoint of change from baseline in KCCQ-CSS, a mixed-effects model repeated measures (MMRM) analysis will be conducted to analyze the change from baseline in the KCCQ-CSS. The analysis will be guided by the treatment policy strategy. All values of the collected KCCQ-CSS data at baseline, 24 weeks, and 52 weeks will be used in the MMRM analysis. The primary endpoint assessment will be the contrast between tirzepatide and placebo at Week 52. The MMRM analysis will be repeated using data during the on-treatment period, which is considered as up to the last dose date plus 7 days.

The MMRM model will include treatment, time (Weeks 24 and 52), treatment-by-time interaction, stratification factors as fixed effects, and baseline value of the KCCQ-CSS as a covariate. Restricted maximum likelihood (REML) will be used to obtain model parameter estimates and the Kenward-Roger option will be used to estimate the denominator degrees of freedom. An unstructured covariance structure will be used to model the within-patient errors. If the analysis fails to converge, the following variance-covariance matrices will be used until convergence is achieved:

- heterogeneous Toeplitz
- heterogeneous first order autoregressive
- heterogeneous compound symmetry
- Toeplitz
- first order autoregressive, and
- compound symmetry.

In the MMRM analysis, the probability of missingness for any postbaseline KCCQ-CSS data that are not collected is assumed only to depend on the observed KCCQ-CSS values.

Change from baseline in the KCCQ-CSS will also be analyzed using an ANCOVA model. The ANCOVA model will include the categorical effect of treatment, stratification factors, and the continuous covariate of baseline KCCQ-CSS value. Missing KCCQ-CSS measurements at Week 52 will be imputed through multiple imputations as specified in Section 3.13.1.3.

3.13.1.5. Additional Analyses for Composite Endpoint of CV Death And HF Event

The contribution of each component of the primary composite endpoint (HF events and CV death) to the overall treatment effect will be examined. Methods similar to those described for the primary analysis will be used to separately analyze the time from randomization to the first occurrence of each component of the primary composite endpoint. The hazard ratio, with its CI and p-value, will be provided.

The CEC-confirmed total number of HF events (first and recurrent) and CV death will be analyzed by the semi-parametric proportional rates model (abbreviated as the LWYY model)

(Lin et al 2000) with treatment as a fixed effect adjusting for diagnosed T2DM (Y/N), baseline probability of HFpEF ($<0.8, \ge 0.8$), and baseline NTproBNP ($<200, \ge 200$ ng/L). A 30-day spacing rule will be applied when consider recurrent events. If an HF event is followed by another within 30 days, these HF events will be considered as a single HF event and the onset date will be the onset of the first HF event. If an HF event is followed by CV death within 30 days, only the CV death will be considered and the onset date will be the onset of the CV death. If an oral diuretic intensification is within 30 days of the date of randomization, it will not be considered as an endpoint. Participants who did not have an adjudicated primary endpoint event on or prior to end of follow-up will be censored at the date of participant's end of follow-up. The rate ratio with 95 confidence interval and p-value will be provided.

Non-parametric estimates of HF event rates over time, allowing for death as terminal event, will be provided (Ghosh and Lin 2000) with treatment as a fixed effect adjusting for diagnosed T2DM (Y/N), baseline probability of HFpEF ($<0.8, \ge0.8$), and baseline NTproBNP ($<200, \ge200 \text{ ng/L}$). A similar spacing rule, as specified in Section 3.13.1.5, will be applied.

Analyses described in Section 3.13.1.2.1.2 for HF events and CV death will be repeated using the investigator's reported events.

3.13.2. Key Secondary Endpoints/Estimands

3.13.2.1. Change from Baseline in 6MWD at Week 52

3.13.2.1.1. Estimand for the Endpoints

The estimand is described by the following attributes:

- Endpoints: Change from baseline to Week 52 in 6MWD
- Treatment condition of interest: tirzepatide MTD vs. placebo
- Handling of intercurrent events: using treatment policy strategy to handle all intercurrent events
- Population: all randomized participants, and
- Population-level summary: median difference between treatment arms.

3.13.2.1.2. Main Analytical Approach

For the key secondary efficacy endpoints of change from baseline in 6MWD at Week 52, the same nonparametric approach as described in Section 3.13.1.1.2, and the same missing data imputation as described in Section 3.13.1.3, will be utilized.

3.13.2.2. Percent Change from Baseline in Body Weight Loss at Week 52

3.13.2.2.1. Estimand for the Endpoint

The estimand is described by the following attributes:

- Endpoint: percent change from baseline to Week 52 in body weight
- Treatment condition of interest: tirzepatide MTD versus. placebo
- Handling of ICEs: using treatment policy strategy to handle all ICEs
- Population: all randomized participants, and

• Population-level summary: the difference in means of the percent change between treatment arms.

3.13.2.2.2. Main Analytical Approach

The percent change from baseline in body weight will be analyzed using an analysis of covariance (ANCOVA) analysis. The ANCOVA model will include the categorical effect of treatment, stratification factors excluding baseline BMI group (<35, ≥35 kg/m²), and the continuous covariate of baseline body weight value.

Missing body weight data at the scheduled postbaseline visits will be imputed using the retrieved dropout approach (as described in Section 3.13.1.3) through multiple imputation. The final statistical inference over multiple imputations will be obtained using the method proposed by Rubin (1987).

3.13.2.3. Change from Baseline in High-sensitivity C-reactive Protein at Week 52

3.13.2.3.1. Estimand for the Endpoint

- Endpoints: change from baseline to Week 52 in hsCRP.
- Treatment condition of interest: tirzepatide MTD versus placebo.
- Handling of ICEs: using the treatment policy strategy to handle all ICEs other than death.
- Population: all randomized participants.
- Population-level summary: the difference in mean change between treatment arms.

3.13.2.3.2. Main Analytical Approach

Change from baseline in hsCRP will be analyzed using an ANCOVA model. The ANCOVA model will include the categorical effect of treatment, stratification factors, and the continuous covariate of baseline hsCRP value. The ANCOVA model will be based on the log-transformed values of hsCRP.

Missing hsCRP at the scheduled postbaseline visits will be imputed using the retrieved dropout approach (as described in Section 3.13.1.3) through multiple imputation. The final statistical inference over multiple imputations will be obtained using the method proposed by Rubin (1987).

3.13.2.4. Sensitivity Analyses for Key Secondary Endpoints

For the change from baseline in 6MWD, a similar MMRM analysis as described in Section 3.13.1.4 will be conducted using data during the on-treatment period.

For percent change from baseline in body weight, a similar MMRM analysis as described in Section 3.13.1.4 will be conducted using data during the on-treatment period.

For the hsCRP change, a similar MMRM analysis as described in Section 3.13.1.4 will be conducted using data during the on-treatment period.

[figure not shown]
Change from baseline in the 6MWD will also be analyzed using an ANCOVA model. The ANCOVA model will include the categorical effect of treatment, stratification factors, and the

continuous covariate of the baseline 6MWD value. Missing 6MWD measurements at Week 52 will be imputed through multiple imputation as specified in Section 3.13.1.3.

3.13.3. Type I Error Rate Control Strategy for Primary and Key Secondary Efficacy Analyses

All primary and key secondary hypotheses will be tested with the overall family-wise type I error rate at a 2-sided alpha level of 0.05 through the multiplicity control approach based on the graphical multiple testing procedure. For the primary hypotheses, the HF outcome will be tested at a 2-sided alpha level of 0.04 and change in KCCQ-CSS will be tested at a 2-sided alpha level of 0.01 in parallel for statistical significance. If significant, the respective alpha of the primary endpoints will be propagated to test the key secondary endpoints. If any of the primary endpoints is not significant, then the appropriate alpha after the key secondary endpoints testing will be recycled to that primary endpoint.

Figure GPID.3.1 provides the details of the graphical multiple testing procedure.

Abbreviations: 6MWD = 6-minute walk distance; HF = heart failure; hsCRP = high-sensitivity C-reactive protein; KCCQ-CSS = Kansas City Cardiomyopathy Questionnaire Clinical Summary Score.

Figure GPID.3.1 Graphical testing scheme for Study GPID.

